## **8.2            *Populations for Analyses***

**All Enrolled Subjects Analysis Set:** This analysis set contains all subjects (including screen failures) who signed an ICF for the study.

**All Treated Subjects Analysis set:** This analysis set includes all subjects who receive either drug.

**Response-evaluable Subjects:** This analysis set includes all subjects who receive either study drug, have a baseline tumor assessment with measurable disease, and 1 of the following: 1) at least 1 evaluable on-treatment tumor assessment, 2) clinical progression, or 3) death prior to the first on-treatment tumor evaluation.

**Enriched Subjects:** This analysis set includes all treated subjects with LAG-3 expression.

**BMS-986016 Pharmacokinetic Analysis Set:** This analysis set includes all subjects who receive BMS-986016 and have at least 1 valid PK parameter to be included in statistical analyses of BMS-986016 PK data.

**BMS-986016 Immunogenicity Analysis Set:** This analysis set includes all subjects who receive BMS-986016 and have baseline and at least 1 postbaseline preinfusion BMS-986016 immunogenicity assessment.

**Nivolumab Immunogenicity Analysis Set:** This analysis set includes all subjects who receive nivolumab and have baseline and at least 1 postbaseline preinfusion nivolumab immunogenicity assessment.

**Pharmacodynamic Analysis Set:** This analysis set includes all treated subjects for whom pharmacodynamic measurements are available at baseline and at least 1 other time point.

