Immediately discontinue infusion of study drug. Begin an IV infusion of normal saline and treat the subject as follows: Recommend bronchodilators, epinephrine 0.2 to 1 mg of a 1:1000 solution for subcutaneous administration or 0.1 to 0.25 mg of a 1:10,000 solution injected slowly for IV administration, and/or diphenhydramine 50 mg IV with methylprednisolone 100 mg IV (or equivalent), as needed. Subject should be monitored until the Investigator is comfortable that the symptoms will not recur. All study drug(s) will be permanently discontinued. Investigators should follow their institutional guidelines for the treatment of anaphylaxis. Remain at bedside and monitor subject until recovery of the symptoms.

In case of late-occurring hypersensitivity symptoms (eg, appearance of a localized or generalized pruritus within 1 week after treatment), symptomatic treatment may be given (eg, oral antihistamine or corticosteroids).

Please refer to [Appendix 4](#) for a complete list of the AE management algorithms.

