### **8.3.2.3 *Immunogenicity***

Incidence of ADA to either BMS-986016 or nivolumab will be assessed during treatment and for up to 135 days after their last treatment in post-treatment follow-up or for a maximum of up to 24 months of treatment, whichever comes first. A baseline ADA-positive subject is defined as a subject with positive seroconversion detected in the last sample before initiation of treatment. An ADA-positive subject is a subject with at least 1 ADA-positive sample relative to baseline after initiation of the treatment.

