#### **8.4.8      *Other Analyses***

##### **8.4.8.1    *Immunogenicity Analyses***

A listing will be provided for all available immunogenicity data. A baseline ADA-positive subject is defined as a subject with positive seroconversion detected in the last sample before initiation of treatment. An ADA-positive subject is a subject with at least 1 ADA-positive sample relative to baseline after initiation of the treatment. For each drug, frequency distribution of baseline ADA-positive subjects and ADA-positive subjects after initiation of the treatment will be summarized. To examine the potential relationship between immunogenicity and safety, a table summarizing the frequency and type of AEs of special interest may be explored by immunogenicity status. In addition, potential relationships between immunogenicity and efficacy and/or PK may also be explored.

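### The immunogenicity sets admit only subjects with a postbaseline preinfusion ADA sample, so early stoppers whose only later sample is the 135-day one are excluded although the ADA endpoint counts that sample

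*Combined protocol and SAP*

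**What the plan says.** Section 8.2 sets two conditions for each immunogenicity set beyond receiving the drug. For relatlimab: "This analysis set includes all subjects who receive BMS-986016 and have baseline and at least 1 postbaseline preinfusion BMS-986016 immunogenicity assessment". For nivolumab, subjects must "have baseline and at least 1 postbaseline preinfusion nivolumab immunogenicity assessment". No reason is given for limiting the postbaseline sample to a preinfusion one.

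Section 8.3.2.3 describes the endpoint without that limit. ADA incidence "will be assessed during treatment and for up to 135 days after their last treatment in post-treatment follow-up", subject to a cap of 24 months of treatment. Positivity is equally broad: "An ADA-positive subject is a subject with at least 1 ADA-positive sample relative to baseline after initiation of the treatment". Section 8.4.8.1 repeats this definition. It adds that all available immunogenicity data will be listed, and that "a table summarizing the frequency and type of AEs of special interest may be explored by immunogenicity status".

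Tables 5.5.1-1 to 5.5.1-5 fix when ADA samples are drawn. All five include a 135-day follow-up sample for both assays, as does the follow-up schedule in Table 5.1-3. Section 5.9.1 also allows serum collected for PK or biomarkers to be tested for ADA ad hoc, for example after a suspected immunogenicity-related event.

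**The concern.** The endpoint counts a sample that the analysis set does not accept for entry. Subjects caught between the two rules are those who leave treatment early, so exclusion is tied to the course of treatment and is not random. A set selected in this way describes ADA in subjects who stayed on treatment at least until the next ADA draw.

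At stake is a secondary objective, the characterisation of immunogenicity, and any exploratory look at ADA status against safety, efficacy or PK that uses these sets. No hypothesis test or decision rule depends on it. The Part D1-Q4W primary safety endpoint is unaffected, because section 8.3.1 divides by treated subjects.

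**Working it through.** **Which ADA samples exist.** The plan states no figure for this point, so the first step is to set the sampling tables beside the set definition.

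- Tables 5.5.1-1 and 5.5.1-2 (Parts A, B Q2W, A1, Part C Q2W, crossover): the first postbaseline ADA sample is the Day 15 predose one.
- Table 5.5.1-3 (Part B Q4W and about the first 6 bladder subjects): Day 29 predose.
- Table 5.5.1-4 (later bladder subjects, D1 Arm 1, later subjects in D1 Arms 2 and 3, D2, E): Day 29 predose.
- Table 5.5.1-5 (first 12 subjects of D1 Arms 2 and 3): Day 29 predose.
- In every table, all later ADA samples are predose except the one at 135-day follow-up, which no infusion follows.

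A subject who stops before the Day 15 or Day 29 draw can therefore supply only the 135-day sample, or an ad hoc sample. Neither meets section 8.2 unless drawn before an infusion. The group is not confined to single-dose subjects: D1 Arm 1 is dosed every 2 weeks but sampled under Table 5.5.1-4, so a subject dosed on Days 1 and 15 who then stops is also excluded.

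**Illustrative size.** Inputs:

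- *n* = 150, the two Part D1-Q4W arms (section 8.1.4.2).
- ADA rate about 21% in combination (section 1.4.1.4.1), applied to the set as an assumption.
- Share stopping before Day 29: not in the documents. A loose proxy is the 2/38 = 5.3% of escalation subjects who progressed between Weeks 1 and 4 (section 3.1.3.1; exact 95% CI 0.6% to 17.7%). Values of 2% and 10% are assumed on either side.

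With *k* excluded subjects and *pos* positives in the set, incidence as written is pos/(n − k). If all *k* gave a 135-day sample and a share *q* of them were positive, incidence would be (pos + q·k)/n.

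| Stop before Day 29 | k | Set as written | q = 0 | q = 0.5 | q = 1 |
|---|---|---|---|---|---|
| 2% | 3 | 31/147 = 21.1% | 31/150 = 20.7% | 32.5/150 = 21.7% | 34/150 = 22.7% |
| 5.3% | 8 | 30/142 = 21.1% | 30/150 = 20.0% | 34/150 = 22.7% | 38/150 = 25.3% |
| 10% | 15 | 28/135 = 20.7% | 28/150 = 18.7% | 35.5/150 = 23.7% | 43/150 = 28.7% |

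With half of the excluded positive, the shift is 0.6, 1.5 and 2.9 percentage points. The largest cell, 7.9 points, needs 10% stopping early and every one of them positive. If the excluded subjects have the same rate as the rest, the shift is nil.

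**How many would return under a wider rule.** Section 1.4.1.4.2 reports 218 deaths within 135 days of last dose among combination-treated subjects, and 876 subjects received the combination: 218/876 = 24.9%. Applying that share, 3, 8 and 15 excluded subjects become about 2, 6 and 11 who could give the sample (3, 8 and 15 × 0.751 = 2.3, 6.0 and 11.3). Early stoppers may die sooner than average, and withdrawal and loss to follow-up reduce the numbers further.

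**The case against.** The best defence is that *preinfusion* merely describes how on-treatment ADA samples are drawn, since all scheduled ones are predose, and that it was never meant to shut out follow-up samples. That may be the intent, but a programmer following section 8.2 would exclude these subjects. The neighbouring pharmacodynamic set asks only for baseline and one other time point, so the restriction reads as a real condition.

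It can also be said that nothing is lost from the report, because all ADA data are listed, and that the Amendment 14 rationale in Appendix 7 calls sampling after discontinuation unnecessary. The first is true of the listing but not of a summary built on the sets. The second does not help, because the current tables and section 8.3.2.3 keep the 135-day sample.

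The objection stands against several stronger readings that a reader might infer:

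- **That the rule removes the severe first-dose reactors, perhaps all of them.** For Grade 3 or 4 infusion reactions section 3.4.4 says "All study drug(s) will be permanently discontinued", whereas section 4.3.5 requires discontinuation for Grade 3 or higher only when the reaction has not returned to Grade 1 within 6 hours. These passages must be reconciled, but under either some subjects could stop at the first dose. For combination therapy, however, section 1.4.1.4.2 mentions only 20 Grade 1 and 31 Grade 2 infusion-related reactions. It does not state that none was more severe. If the count were 0/876, the exact 97.5% upper bound would be 1 − 0.025^(1/876) = 0.42%, or about 0.3 subjects per arm of 75 over all doses.
- **That these subjects are the most informative about ADA and reactions.** An ADA result obtained 135 days later postdates a first-dose reaction and cannot explain it; only baseline ADA precedes it. The table by ADA status is also optional.
- **That their baseline ADA results are necessarily lost.** Section 8.4.8.1 names no denominator for baseline ADA, so this is possible but not established.
- **That every early stopper is wrongly excluded.** The 135-day sample is scheduled, not assured. Subjects with no postbaseline sample are properly outside the set.

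**Conclusion.** The inconsistency between sections 8.2 and 8.3.2.3 is real. As written, both immunogenicity sets exclude subjects who stop before the first postbaseline predose ADA draw and whose only postbaseline sample is the 135-day one, or an ad hoc one not drawn preinfusion. The endpoint counts those samples, and the exclusion depends on early discontinuation.

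The size is modest and rests on assumptions, since the documents give no count. With 2% to 10% of 150 D1-Q4W subjects stopping before Day 29, 3 to 15 are dropped, fewer of them wrongly where no 135-day sample is obtained. The likely effect on ADA incidence is a few percentage points at most, and none if these subjects resemble the rest. The early-progression proxy comes from escalation cohorts and is not a discontinuation rate; section 4.3.4 permits treatment beyond progression. The point merits correction because the set and the endpoint should agree, not because a large bias has been shown.

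**What to change.** In section 8.2, for both immunogenicity sets, replace the postbaseline preinfusion requirement with at least one postbaseline assessment, on treatment or in follow-up. In section 8.4.8.1, tabulate baseline ADA status on all treated subjects with a baseline sample, and name the amended sets as the denominator for ADA after treatment start.

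This is a wording change. The samples and assays are already planned. The only downside is a slightly different denominator.

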## 8.3 Endpoints

### 8.3.1 Primary Endpoints

The primary endpoint of this Phase 1/2a study is safety as measured by the rate of AEs, SAEs, AEs leading to discontinuation of treatment, deaths, and laboratory abnormalities assessed during treatment and for up to 135 days of follow-up. All subjects who receive at least 1 dose of BMS-986016 or nivolumab will be analyzed for safety.

The coprimary endpoints in Part C are ORR, DCR, and DOR based on BICR assessments using RECIST v1.1, where applicable, in selected disease cohorts.

The coprimary endpoint in Part D1-Q2W is ORR, as determined by BICR using RECIST v1.1, in advanced melanoma subjects with LAG-3 expression who progressed while on anti-PD-1 antibody therapies.

- ORR is defined as the total number of subjects whose BOR is either CR or PR divided by the total number of treated subjects in the population of interest.

Best overall response per RECIST v1.1 is defined as the best response designation recorded between the date of first dose and the date of first objectively documented progression per RECIST v1.1 or the date of subsequent therapy, whichever occurs first. CR or PR determinations included in the BOR assessment must be confirmed by a second scan no less than 4 weeks after the criteria for response are first met. For subjects who continue treatment beyond progression per RECIST v1.1 or begin subsequent therapy, the BOR should be determined based on response designations recorded up to the time of the initial progression or subsequent therapy, whichever occurs first. For subjects without documented progression or subsequent therapy, all available response designations should contribute to the BOR assessment.

- DCR is defined as the total number of subjects whose BOR is either CR, PR, or SD for at least 12 weeks divided by the total number of treated subjects in the population of interest.

DOOR computed only for subjects with a BOR of CR or PR is defined as the number of days between the date of first response and the date of first objectively documented disease progression based on the criteria (RECIST v1.1) or death, whichever occurs first. For those subjects who neither progress nor die, the duration of objective response will be censored at the same time they will be censored for the primary definition of PFS (see [Section 8.3.2.2](#)).

The primary endpoint in Part D1-Q4W of the study is the incidence of AEs in the Broad Scope MedDRA Anaphylactic Reaction SMQ occurring within 2 days after dosing. This incidence rate is defined as number of subjects who experienced at least 1 AE in the Broad Scope MedDRA Anaphylactic Reaction SMQ with onset on the day of or within 2 days after any study therapy infusion divided by number of treated subjects. The terms included in the MedDRA Anaphylactic Reaction SMQ based on the most current MedDRA version will be listed in the statistical analysis plan (see [Appendix 5](#)).

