**Table 5.1-3: Follow-up Procedural Outline Parts A Through E**

Procedure	Clinical Follow-up			Survival Follow-up	Notes
	FU 1 30 days a (± 5 days)	FU 2 60 days a (± 5 days)	FU 3 135 days a (± 5 days)		
Immunogenicity (ADA) assessments			X See Notes		See Table 5.5.1-1 and Table 5.5.1-2 for Q2W. See Table 5.5.1-3 for Q4W; see Table 5.5.1-4 / Table 5.5.1-5 for Part D and Part E.
Efficacy Assessments					
Diagnostic imaging	X See Notes			X See Notes	Diagnostic imaging required by method used at baseline; an unconfirmed PR, unconfirmed CR, or unconfirmed PD must be confirmed ≥ 4 weeks after initial assessment. Q12W diagnostic imaging must be performed in subjects who discontinue study treatment, at Investigator's discretion, with CR, PR, or SD by RECIST v1.1, until disease progression. Images will be acquired until withdrawal of consent, death, or initiation of another anticancer treatment.
Response assessment	X See Notes				Assessed by RECIST v1.1; see Appendix 2 .

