### **8.3.2.2 *Efficacy***

The BOR, ORR, DCR, DOR, and PFS rates at prespecified time points (eg, 24 weeks) based on Investigator assessment using RECIST v1.1 will be the secondary efficacy endpoints. The efficacy endpoints based on BICR assessment, where applicable (ie, not designated as the primary), will also be the secondary efficacy endpoints.

BOR, ORR, DCR, and DOR were defined under the primary endpoints. Progression Free Survival is defined as the time from first dose to the date of first objectively documented progression, per RECIST v1.1, or death due to any cause, whichever occurs first. Clinical deterioration in the absence of objectively documented progression per RECIST v1.1 is not considered progression for the purpose of determining PFS. Subjects who die without a reported progression will be considered to have progressed on the date of their death. Subjects who did not progress or die will be censored on the date of their last evaluable tumor assessment. Subjects who did not have any on study tumor assessments and did not die will be censored on the date of first dose. Subjects who started any subsequent anticancer therapy, including tumor-directed radiotherapy and tumor-directed surgery, without a prior reported progression will be censored at the last evaluable tumor assessment prior to initiation of the subsequent anticancer therapy. The PFS rate at time T is defined as the probability that a subject has not progressed and is alive at time T following first dose.

Landmark 1-year and 2-year OS rates will be assessed as secondary efficacy endpoints in Part D.

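### DOR is censored before new anticancer therapy only if the responder has no later progression or death, and the PFS rules do not say what happens when a subject switches and then dies

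*Combined protocol and SAP*

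**What the plan says.** Section 8.3.1 gives DOR coprimary status in part of the study: "The coprimary endpoints in Part C are ORR, DCR, and DOR based on BICR assessments using RECIST v1.1, where applicable, in selected disease cohorts". In Parts D and E it is a secondary endpoint (Sections 1.3.2 and 8.3.2.2). A response ends at "the date of first objectively documented disease progression based on the criteria (RECIST v1.1) or death, whichever occurs first". Subsequent therapy is not mentioned. Censoring is then borrowed from PFS for one group only: "For those subjects who neither progress nor die, the duration of objective response will be censored at the same time" as for PFS, with a cross-reference to Section 8.3.2.2.

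Section 8.3.2.2 has three PFS rules that bear on this:
- A death with no progression on record is an event on the day of death.
- "Subjects who did not progress or die will be censored on the date of their last evaluable tumor assessment".
- "Subjects who started any subsequent anticancer therapy, including tumor-directed radiotherapy and tumor-directed surgery, without a prior reported progression" form a further group, who "will be censored at the last evaluable tumor assessment prior to initiation of the subsequent anticancer therapy".

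No order of precedence is given between the first rule and the third. Table 5.1-3 limits scheduled imaging: "Images will be acquired until withdrawal of consent, death, or initiation of another anticancer treatment". Survival follow-up continues for up to 5 years from first dose (Section 3.1). Section 8.4.2 prescribes Kaplan-Meier for both DOR and PFS.

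**The concern.** Kaplan-Meier needs the decision to censor at a given time to rest on what is known by that time. Under the DOR sentence, two responders with identical histories up to the switch are treated differently according to what happens afterwards. The one who later dies stays in the risk set until death and counts as an event. The one who survives is removed at the last scan before the switch. Follow-up after the switch is thus kept mainly for those who fail.

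The PFS overlap means that two programmers can apply the text correctly and produce different PFS and DOR datasets. DOR also feeds judgements beyond its own estimate: further expansion of Part C cohorts (Section 8.1.3) and the choice of LAG-3 cutpoint (Section 8.4.2).

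**Working it through.** **Rules applied to one subject.** The plan states no figure on this point, so there is none to reproduce. Take an illustrative responder: first response at week 8, last scan at week 24, new therapy at week 26 without progression. PFS runs from first dose and DOR from first response.

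| What happens next | DOR as written | PFS if new-therapy rule prevails | PFS if death rule prevails |
|---|---|---|---|
| Dies at week 80, no progression | event at 80 − 8 = 72 weeks | censored, week 24 | event, week 80 |
| Alive at cut-off, no progression | censored at 24 − 8 = 16 weeks | censored, week 24 | censored, week 24 |
| Progression documented after the switch | event on that date | censored, week 24 | censored, week 24 |

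- The DOR column depends on the later outcome under either PFS reading.
- If the new-therapy rule prevails, DOR and PFS disagree for the subject who dies.
- If the death rule prevails, they agree for that death, but PFS now has the same dependence on later outcome (row 1 against row 2).
- Progression after a switch is a DOR event and a censored PFS observation under both readings. Most later events will be deaths, because scheduled scans stop. The progression route remains open: Section 8.3.2.2 counts tumor-directed radiotherapy as subsequent therapy, Section 3.4.3.1 allows palliative radiotherapy with study drug resumed afterwards, and on-treatment scans continue every 8 weeks (Table 5.1-2). It applies if such radiotherapy is classed as tumor-directed.

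**Illustrative size.** All inputs are assumptions: exponential time from response to progression with median 12 months; an independent exponential switch time; exponential survival after the switch with median 6, 12 or 24 months; scans every 8 weeks; no progression captured after the switch; 24-36 months of follow-up from response; 200,000 simulated responders per scenario. Aligned means every switcher is censored at the last scan before the switch. Literal means the text of Section 8.3.1.

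| Switchers | Median survival after switch (months) | 24-month DOR, aligned | 24-month DOR, literal | Difference (points) | Median DOR (months), aligned / literal | Switchers changed from censored to event |
|---|---|---|---|---|---|---|
| 9% | 6 | 0.248 | 0.228 | 2.0 | 11.9 / 11.5 | 83% |
| 9% | 12 | 0.248 | 0.237 | 1.1 | 12.0 / 11.9 | 64% |
| 8% | 24 | 0.247 | 0.241 | 0.6 | 11.9 / 11.9 | 41% |
| 18% | 6 | 0.246 | 0.206 | 4.0 | 11.9 / 11.2 | 84% |
| 18% | 12 | 0.247 | 0.223 | 2.4 | 11.9 / 11.7 | 65% |
| 18% | 24 | 0.245 | 0.232 | 1.3 | 11.8 / 11.8 | 42% |
| 27% | 6 | 0.242 | 0.177 | 6.5 | 11.7 / 10.8 | 85% |
| 27% | 12 | 0.242 | 0.202 | 4.0 | 11.8 / 11.5 | 66% |
| 27% | 24 | 0.243 | 0.221 | 2.2 | 11.7 / 11.8 | 43% |

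The literal rule lowers the 24-month probability in every scenario. The median changes by between −0.9 and +0.1 month. At 12 months, with slow deaths after the switch, the literal curve can sit a fraction of a point higher (0.495 against 0.494; 0.493 against 0.491), because subjects who die later are held at risk meanwhile.

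**Leverage of one subject.** The Part C melanoma cohort reported 7 responders among 61 (Section 1.1.6). One reclassified responder is 1/7 = 14% of that curve.

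**The case against.** The best defence is that alignment was intended. The DOR sentence points to the PFS section, best overall response already stops at subsequent therapy (Section 8.3.1), and the limiting phrase could be shorthand for having no PFS event. The intention is plausible, but the wording does not deliver it: Section 8.3.2.2 lists subjects without progression or death separately from those who start new therapy. The protocol defers some detail to a statistical analysis plan, but no text available here settles the point.

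Three further objections limit the point:

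- **Precedence.** A reader might infer that the response of anyone who switches and later dies outlasts their PFS. The documents do not support that for deaths, because the death rule in Section 8.3.2.2 may prevail over the new-therapy rule. It does hold for progression documented after a switch.
- **Size.** No switch rate is documented. Other anticancer therapy is prohibited during treatment (Section 3.4.1), and responders who stop at the investigator's discretion are scanned every 12 weeks until progression (Section 3.1). Both should limit switching before progression. Sampling error is also larger than the effect: with the 16-20 responders in the 90-subject rows of Table 8.1.4.1-2 and a 24-month rate near 0.25, the uncensored 95% half-width is 1.96 × √(0.25 × 0.75 / n), or 21 points at n = 16 and 19 points at n = 20.
- **Weight.** DOR is coprimary only where applicable in selected Part C cohorts, the Part C stage thresholds count responses, and no formal hypotheses are evaluated (Section 1.2).

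These points reduce the consequence. They do not make the censoring valid.

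**Conclusion.** The point holds as a defect of definition. As written, DOR censoring for responders who switch without progression depends on their later outcome, and the PFS section leaves a switch followed by death without a determinate result. Neither precedence reading repairs this: one makes DOR and PFS disagree, and the other gives PFS the same fault.

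Under the assumed scenarios the effect is 0.6-6.5 points lower at 24 months and less than 1 month on the median. The range is driven by the assumed switch rate and survival after the switch. A reader might infer that counting time on the next treatment inflates DOR in the drug's favour. An individual duration can be much longer, but the average effect at 24 months runs the other way, because the rule keeps the deaths and drops the survivors. The case for change is validity and reproducibility, most of all in cohorts with few responders.

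**What to change.** 1. **Section 8.3.2.2:** state that subjects who start subsequent anticancer therapy without prior progression are censored at the last evaluable assessment before it, regardless of later progression or death, and that this takes precedence over the death rule.
2. **Section 8.3.1:** replace the DOR censoring sentence with: *DOR uses the PFS event and censoring rules for all responders.* Apply it to central and investigator assessments wherever DOR is analysed. Changing this sentence alone would not be enough, because the precedence question would carry over from PFS.
3. **Supportive analysis:** for both endpoints, ignore subsequent therapy, so that later documented progression or death counts for everyone and no one is censored at the switch. Note beside it that scheduled imaging stops at new therapy, so progression after a switch will be under-recorded.

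The cost is wording in two sections, matching text in the statistical analysis plan and one extra set of outputs. No new data are needed: Table 5.1-3 already has the start dates of new anticancer therapies recorded during survival follow-up.
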